Chronic kidney disease, an inpairment in kidney function beyond age-expected decline, is commonly attributed to kidney damage from diabetes mellitus and/or hypertension. While the direct mechanism(s) of kidney injury resulting from these comorbidities has yet to be defined, it has been hypothesized that the vasculature is involved in kidney function. This hypothesis is supported by the evidence that the one proven therapy for chronic kidney disease, namely angiotensin converting enzyme inhibitors (ACEIs) or angiotensin receptor blockers (ARBs), improves vascular function.

In our study of patients with resistant hypertension, we have shown that vascular function improves with the use of spironolactone, a mineralocorticoid receptor antagonist. Spironolactone has also been shown to reduce urinary protein loss in patients with chronic kidney disease. Therefore, it is reasonable to suppose that spironolactone can improve vascular function in patients with chronic kidney disease. Currently spironolactone is used sparingly in early stages of chronic kidney disease and is avoided in late stages of chronic kidney disease due to the risk of raising serum potassium levels. If spironolactone improves vascular function in patients with moderate stages of chronic kidney disease, as it has been shown to do in patients with resistant hypertension, then defining this mechanism would open new therapeutic avenues for patients with chronic kidney disease.

15. Participants (Screening and Selection)

a. How many participants are to be enrolled at UAB? 62 If multi-center study, total number at all centers:

b. Sex: 50% Male

Race/Ethnicity: All races and ethnicities in the Birmingham area will be enrolled. Enrollment is expected to be composed of 65% African American (chronic kidney disease is more prevalent among African Americans).

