Exclusion Criteria	 Severe HTN (office BP ≥ 160/100 mm Hg) Hypotension (office BP < 110/70 mm Hg) Serum potassium > 5 mEq/L History of arrhythmia, including atrial fibrillation Pregnant or breast feeding woman DM type 1 DM type 2 with hemoglobin A1C ≥ 6.5 % Dementia or cognitive impairment prohibiting informed consent History of ischemic stroke, unstable angina, or myocardial infarction within the past 6 months Allergy or intolerance to spironolactone or amiloride Use of an MR antagonist or an epithelial sodium channel blocking medication within the last month 				

Describe the inclusion/exclusion criteria:

ACR = albumin-to-creatinine ratio, HTN = hypertension, BP = blood pressure, DM = diabetes mellitus, MR = mineralocorticoid receptor

Patients with severe hypertension (office BP > 160/100 mm Hg) are excluded due to 1) the possibility of requiring blood pressure medication changes during the study period, 2) direct effects of blood pressure on vascular function testing, and 3) increased cardiovascular risk leading to potential serious adverse events. Patients with hypotension (office BP < 110/70 mm Hg) were excluded due to an expected drop in blood pressure with administration of spironolactone and/or amiloride.

- d. If participants will comprise more than one group or stratification, describe each group (e.g., treatment/intervention, placebo, controls, sham treatment) and provide the number of participants anticipated in each group.
 This clinical trial follows a cross-over design. All participants are scheduled to receive both study medications in series with randomization to the initiating therapy (See Figure 2).
- e. Indicate which, if any, of the special populations listed below will be involved in the protocol. Include the Special Populations Review Form (SPRF) if indicated.
 Pregnant Women: Attach SPRF—Pregnant Women, Fetuses,
 - Neonates/Nonviable Neonates
 - Fetuses: Attach SPRF—Pregnant Women, Fetuses, Neonates/Nonviable Neonates
 - Neonates/Nonviable Neonates: SPRF—Pregnant Women, Fetuses, Neonates/Nonviable Neonates
 - Prisoners: Attach SPRF—Prisoners
 - Minors (<19 years old): Attach SPRF—Minors
 - Employees or students at institution where research conducted
 - Persons who are temporarily decisionally impaired

Persons who are permanently decisionally impaired (e.g., mentally retarded)
Non-English Speakers

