Study participants with proteinuric, CKD will be randomly assigned in a double-masked fashion to spironolactone 25mg daily or amiloride 5 mg daily for 6 weeks and then crossed over to the alternate study medication after a 1 month wash-out period (See Figure 1). Vascular function will be assessed at baseline and the end of each 6 week treatment period by: 1) ultrasound guided flowmediated dilation (FMD) of the brachial artery, 2) impedence cardiography, 3) pulse-wave velocity, 4) 24 hour ambulatory blood pressure monitoring, and 5) serum and urine biomarkers. Participants will undergo a total of 7 visits over 16-18 weeks; 3 of the 7 visits will involve vascular function testing.

Pulse-wave velocity is measured non-invasively with placement of a small sensor (tonometry probe) over the carotid and femoral artery. This procedure poses no discomfort and is usually done in about 15 minutes. Impedence cardiography is also noninvasive with minimal inconvenience to the participant. It is performed by placing small electrode pads on the chest wall and neck and takes about 12 minutes. FMD is measured by assessing the change in brachial artery diameter by ultrasound. A blood pressure cuff is placed below the elbow and inflated above systolic blood pressure for 5 minutes. The cuff is then released and change in brachial artery is determined immediately afterwards for 2 minutes. The entire procedure takes about 45 minutes. Some back discomfort can occur with FMD testing as participants must lie flat for 30 minutes. Hand and arm discomfort from cuff inflation is common yet resolves immediately after cuff deflation. Collection of urine for 24 hours and wearing a blood pressure monitor for 24 hours can be disruptive to normal daily/nightly activities; however poses no danger or long-term inconvenience.

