A study visit where vascular function testing is to be performed will begin at 0800 in the morning and start with a vital sign assessment including height, weight, body fat percent, and left arm automated BP measurement followed by confirmation of fasting status and a brief past medical history. Each participant will then lie supine for 10 minutes in preparation for vascular function testing. Following the pulse wave velocity, impedence cardiography, and FMD measurements, the participant will have his/her blood and urine collected for laboratory testing. Laboratory testing will include ~20 mL of blood for plasma and serum testing. Participants will return 24 hour urine samples and have a 24 hour ambulatory monitor placed. This entire visit is expected to take 2 hours.

Study visits where vascular function testing will not be performed (e.g., screening visit, visit 2, visit 4, and visit 5; see Table 2) should last 30 minutes and involve a medication assessment, vital sign check, and blood collection for serum potassium (~4 mL).

All study medication will be prepared by the UAB Research Pharmacy in matching capsules.. The order of medication dispensing will follow simple randomization using an *a priori* randomization list prepared by the research pharmacy.

[figure not shown]

Figure 1: Study design

VFT = vascular function testing (i.e., ultrasound assessed flow-mediated dilation and biomarker measurement), 24hrU = 24 hour urine collection, 24hrABPM = 24 hour ambulatory blood pressure monitoring, K = potassium *30-60 mL/min/1.73m² eGFR by MDRD, proteinuria defined as ACR \geq 30 mg/g

- b. What is the probable length of time required for the entire study (i.e., recruitment through data analysis to study closure)?
 5 years
- **c.** What is the total amount of time each participant will be involved? 16 weeks

- **d.** If different phases are involved, what is the duration of each phase in which the participants will be involved? If no phases are involved, enter "not applicable." The cross-over design consists of two 6 week intervention periods separated by a one month washout period.
- **e.** List the procedures, the length of time each will take, and the frequency of repetition, and indicate whether each is done solely for research or would already be performed for treatment or diagnostic purposes (routine care) for the population. *Insert additional table rows as needed.*

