Table 2. Combined study procedure schedule								
	Screen Visit	Visit 1	Visit 2	Visit 3	Visit 4	Visit 5	Visit 6	
	Week -(1-2)	Week 0	Week 2	Week 6	Week 10	Week 12	Week 16	
Informed consent	Х							
Study medication pill count			Х	Х		Х	Х	
Con medication assessment		Х		Х	Х		Х	
Dispense study medication		Х			Х			
Clinic vital signs	Х	Х	Х	Х	Х	Х	Х	
FMD		Х		Х			X	
ACR	Х	Х		Х			X	
RFP	Х			Х			X	
24 hour ABPM		Х		Х			Х	
Plasma aldosterone, PRA		Х		Х			Х	
Blood & urine biomarkers*		Х		Х			Х	
Serum potassium via BMP			Х		Х	Х		
24hr urine collection		Х		Х			Х	
Urine Pregnancy Test	Х							
Con = concomitant, FMD = flow-mediated dilation, ACR = spot urinary albumin-to-creatinine ratio, RFP = renal function panel, PRA = plasma renin activity, BMP = basic metabolic panel, ABPM = ambulatory blood pressure monitor *Biomarkers include serum high-sensitivity C-reactive protein (hsCRP), serum pentraxin-3 (PTX-3), serum fetuin-A, serum uric acid, plasma asymmetric dimethylarginine (ADMA), serum soluable vascular cell adhesion molecule (sVCAM-1), homeostasis model assessment method of insulin resistance (HOMA-IR), plasma and urine F2-								
isoprostanes, and plasma endothelin.								

All procedures will be for research purposes. Study visits 1, 3, and 6 will be approximately 120 minutes in length. Study visits 2, 4, and 5 will be approximately 30 minutes in length.

- **f.** Will an interview script or questionnaire be used? □Yes ⊠No **If Yes**, attach a copy.
- **g.** Will participants incur any costs as a result of their participation? **If Yes**, describe the reason for and amount of each foreseeable cost.
- **h.** Will participants be compensated?

If Yes, complete i-v:

i. Type: (e.g., cash, check, gift card, merchandise): Check

ii. Amount or Value: \$100 for the study visits 1, 3, and 6 and \$50 for study visits 2, 4, 5, screening visit, and unscheduled visit(s).

iii. Method (e.g., mail, at visit): Mail

iv. Timing of Payments: (e.g., every visit, each month): After the visit

v. Maximum Amount of Payments per Participant: \$500 (not including any unscheduled visits)

🔄 Yes 🖂 No

Yes No

17. Describe the potential benefits of the research.

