There is no anticipated direct benefit which the participants will obtain from participating in the protocol. However, indirect benefits may include discovering that spironolactone or amiloride reduces albuminuria and/or blood pressure. In addition, participants who experience an improvement in endothelial function with spironolactone use would be expected to have a lower cardiovascular risk with continued use. We feel the risks involved with participating in this study are reasonable in relation to the potential benefits.

18. Risks

- a. List the known risks—physical, psychological, social, economic, and/or legal—that participants may encounter as a result of procedures required in this protocol. Do not list risks resulting from standard-of-care procedures. Note. Risks included in this protocol document should be included in the written consent document. No undue hazards (physical, psychological, financial, legal, or other) are anticipated with vascular function testing or blood and urine sampling. Participants may be exposed to several potential risks as itemized below:
 - 1. Hyperkalemia: Administration of both spironolactone and amiloride are associated with increases in serum potassium of approximately 0.4 mEq/L. Serum levels of potassium will be monitored at each study visit. Kayexalate and a low potassium diet will be administered for levels of serum potassium > 5.5 meq/L followed by a repeat potassium level in 3 days. Participants will be withdrawn from the study with serum potassium levels > 6.0 meq/L. In addition, participants will not be allowed to participate in the second treatment period with a serum potassium > 5.0 meq/L when checked at week 10.
 - 2. Fetal toxicity: Spironolactone is associated with fetal toxicity. Pregnant women, as determined by a screening urine sample, are excluded from study participation. Women of child bearing potential will be advised of the risk of fetal toxicity, and if a pregnancy occurs during the study the participant will be withdrawn and study medication stopped.
 - 3. Gynecomastia: Spironolactone is associated with breast growth in men. This association occurs more frequently with the long-term use of doses exceeding 50mg/day.
 - 4. Discomfort and risks (hematoma/skin infection) associated venous blood collection

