 - **ii.** Describe any other alternative treatments or interventions: An angiotensin converting enzyme inhibitor (ACEI) or an angiotensin receptor blocker (ARB) is recommended for patients who have CKD and moderate levels of albuminuria and/or uncontrolled hypertension. Participation in this clinical trial will not interfere with this therapy.
 - iii. Describe any withholding of, delay in, or washout period for standard of care or alternative treatment that participants may be currently using: Patients taking spironolactone, amiloride, or triamterene at baseline will be offered to hold this medication for 1 month prior to starting the study. All participants will undergo a 1 month washout between the 2 intervention periods.
- d. Do you foresee that participants might need additional medical or psychological resources as a result of the research procedures/interventions? Yes No If Yes, describe the provisions that have been made to make these resources available.
- e. Do the benefits or knowledge to be gained outweigh the risks to participants?

⊠Yes □No

🖂 Yes 🗌 No

If No, provide justification for performing the research:

19. Precautions/Minimization of Risks (If study involves drugs or devices complete the Drug or Device Review Sheet and skip to question #20)

- **a.** Describe precautions that will be taken to avoid risks and the means for monitoring to detect risks.
- **b.** If hazards to an individual participant occur, describe (i) the criteria that will be used to decide whether that participant should be removed from the study; (ii) the procedure for removing such participants when necessary to protect their rights and welfare; and (iii) any special procedures, precautions, or follow-up that will be used to ensure the safety of other currently enrolled participants.
- **c.** If hazards occur that might make the risks of participation outweigh the benefits for all participants, describe (i) the criteria that will be used to stop or end the entire study and (ii) any special procedures, precautions, or follow-up that will be used to ensure the safety of currently enrolled participants.

20. Informed Consent

- a. Do you plan to obtain informed consent for this protocol? Xes No
 If Yes, complete the items below.
 If No, complete and include the Waiver of Informed Consent or Waiver of Authorization and Informed Consent, as applicable.

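### Does the lack of an off-drug measurement after the washout undermine what Sections 14 and 17 say the trial may show?

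*Protocol*

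**What the plan says.** Section 16a randomises participants "to spironolactone 25mg daily or amiloride 5 mg daily for 6 weeks and then crossed over to the alternate study medication" after a one-month washout. Section 15d confirms that only the order is random: "All participants are scheduled to receive both study medications in series with randomization to the initiating therapy". Section 18c iii repeats the break: "All participants will undergo a 1 month washout between" the two periods.

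Under Section 16a, vascular function is "assessed at baseline and the end of each 6 week treatment period". Table 2 in Section 16e agrees. Flow-mediated dilation, 24-hour ambulatory blood pressure and biomarkers fall at Visits 1, 3 and 6 (weeks 0, 6 and 16). ACR, a spot urine test ("ACR = spot urinary albumin-to-creatinine ratio"), falls at screening and at the same three visits. Visit 4 (week 10) is one of the short visits that "involve a medication assessment, vital sign check, and blood collection for serum potassium". Study medication is also dispensed there, and no urine is tested.

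Two sentences speak of a drug's effect without naming a comparator. Section 14 opens its closing rationale with "If spironolactone improves vascular function in patients with moderate stages of chronic kidney disease". Section 17, on potential benefits, says that "indirect benefits may include discovering that spironolactone or amiloride reduces albuminuria and/or blood pressure".

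**The concern.** No participant is randomised to placebo or to no treatment. Once dosing starts, ACR and the vascular measures have no further off-drug value. A statement about what one drug does to albuminuria or vascular function could then rest only on uncontrolled change from baseline.

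Two misreadings would be possible. If both drugs helped equally, the randomised contrast would be null and might be read as spironolactone having no effect. Alternatively, drift over 16 weeks might be credited to a drug. For scale, assume a drift of 0.1, 0.2 or 0.3 standard deviations of the change. A two-sided 5% before-after test in 62 people would then wrongly report improvement in 12%, 34% or 64% of trials. Eligibility also requires ACR above a threshold (Table 1), which invites regression to the mean from the screening value. Since Visit 4 takes place anyway, a spot urine there looks like a cheap remedy.

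**Working it through.** The protocol gives no figure on this point, so there is none to reproduce. The inputs are the visit weeks (0, 6, 10, 16) and the 62 participants of Section 15a. Drift, effect sizes and carryover below are assumptions.

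**1. The schedule.** The reading of Table 2 is correct: ACR and the vascular measures are blank at week 10. Clinic vital signs are not blank, so clinic blood pressure, one of the two outcomes in the Section 17 sentence, does have an off-drug value after the washout.

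**2. The randomised contrast.** Let S and A be the two drug effects and b a drift per week. Week 6 minus week 16 is:

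- spironolactone first: (S + 6b) − (A + 16b) = (S − A) − 10b
- amiloride first: (A + 6b) − (S + 16b) = −(S − A) − 10b

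Half the difference between the sequences is S − A. Drift cancels, and no week-10 value enters.

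**3. What a week-10 ACR would change.** Change from week 0 carries a drift of 6b in period 1 and 16b in period 2, on average (6b + 16b)/2 = 11b. Measured from the preceding off-drug value, it is 6b in both periods. With a total drift D = 16b these are 11/16 = 0.6875D and 6/16 = 0.375D. The bias shrinks but stays, because drug versus no drug is still a before-after comparison.

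A simulation with assumed log-ACR effects of −0.30 (spironolactone) and −0.20 (amiloride) and b = −0.01 agrees:

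- spironolactone minus amiloride: −0.10, the true value
- spironolactone against week 0: −0.41 (−0.30 − 0.11)
- spironolactone against its own preceding off-drug value: −0.36 (−0.30 − 0.06)

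**4. Precision.** The model is linear with fixed participant effects, equal sequences and independent errors. The table gives the variance of one drug's own effect, relative to that of the spironolactone–amiloride contrast (1.00 in every cell).

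| Drift allowed for | Weeks 0, 6, 16 | With week 10, no carryover | With week 10, drug-specific carryover at week 10 |
|---|---|---|---|
| none | 1.00 | 0.75 | 1.00 |
| linear | 2.21 | 0.93 | 2.21 |
| quadratic | not estimable | 0.93 | not estimable |
| free time effects | not estimable | not estimable | not estimable |

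The gain in the third column requires that nothing of the first drug's effect remains at week 10. Once carryover is estimated, the week-10 value is used up in estimating it, and the figures return to those without the sample. The same sample cannot both test the washout and serve as a clean baseline.

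**5. Regression to the mean.** Selection on ACR most naturally acts through the screening value, and Table 2 already repeats ACR at week 0. If within-person errors are independent, as in step 4, the week-0 value is not affected by that selection.

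**6. The two sentences.** Section 14 is a conditional in a lay background section. Section 17 answers a form question about benefits and says only what these may include. Neither states an objective, an endpoint or an analysis, so neither conflicts with Section 16a or Table 2.

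**The case for a change.** The best case for the point is practical. An analysis plan can say how change from baseline will be handled, but it cannot supply a urine sample that the schedule does not collect. The crossover relies on its washout, and for albuminuria nothing checks it. At most 62 spot urines at a visit already attended would give a 95% interval for the week-10 minus week-0 change with a half-width of 0.25 standard deviations of that change (0.28 if an assumed 50 people reach week 10).

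That much stands: a week-10 ACR would be informative about carryover in that one outcome. It does not make the plan deficient. With carryover of a fraction λ of the first drug's effect into week 16, the contrast becomes (S − A)(1 − λ/2). An assumed 25% moves −0.10 to about −0.088, which is a modest attenuation toward zero. The period-2 outcome is in any case read at week 16, ten weeks after the first drug ends at week 6. The sample would do nothing for flow-mediated dilation, pulse-wave velocity or ambulatory blood pressure, which are the trial's vascular measures.

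The risk of misreading a null contrast is also real, but every active-comparator trial shares it. It is a matter for interpreting the result, and no sentence in this protocol makes that mistake.

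**Conclusion.** The concern is not upheld. The factual reading is right: ACR and the vascular measures have no off-drug value after week 0, and only spironolactone versus amiloride is a randomised comparison. But the first fact does not cause the second. Single-drug effects are uncontrolled because no untreated period is randomised, and a week-10 measurement would leave them so.

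The randomised contrast is free of common drift without that measurement and has the same variance either way. The apparent gain for one drug's own effect (2.21 to 0.93 under linear drift) assumes zero carryover at week 10 and disappears when that assumption is dropped. An active-comparator crossover is a legitimate design, and Sections 14 and 17 make no inferential claim that it fails to support. An extra urine sample is an option the investigators may weigh; its absence is not an error. The conclusion rests on reading those two sections as lay text and on leaving the analysis of within-drug change to an analysis plan that is not shown.

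### The only pregnancy test is at screening, so it is 11 to 12 weeks old when women randomised to amiloride first start spironolactone at week 10

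*Protocol*

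**What the plan says.** Item 18.a.2 of the Protocol associates spironolactone with fetal toxicity and states that pregnant women, as "determined by a screening urine sample, are excluded from study participation"; item 18.b.2 repeats this. Item 18.a.2 adds that women of "child bearing potential will be advised of the risk of fetal toxicity, and if a pregnancy occurs" the participant is withdrawn and drug is stopped.

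Table 2 (item 16.e) agrees. The row "Urine Pregnancy Test" has a single mark, in the screening column. The row "Dispense study medication" has two, at Visit 1 (week 0) and Visit 4 (week 10). Under item 16.a, participants take one drug for six weeks and are then "crossed over to the alternate study medication after a 1 month wash-out period", so Visit 4 is where the second drug starts.

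Item 16.a describes the visits without vascular testing, Visit 4 among them, as ones that "involve a medication assessment, vital sign check, and blood collection for serum potassium (~4 mL"). The short medical history belongs to the vascular-testing visits, of which Visit 3 (week 6) is the last before the second drug starts.

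Potassium is handled differently. Under item 18.a.1, "participants will not be allowed to participate in the second treatment period with a serum potassium > 5.0 meq/L when checked at week 10".

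**The concern.** In a crossover, the second dispensing is a second start of treatment. For women randomised to amiloride first, it is the first exposure to the drug that the protocol links to fetal harm. The check meant to keep pregnant women off that drug was made before period 1 and is not repeated after six weeks of treatment and a month of washout.

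The withdrawal rule acts only once a pregnancy is known, and no scheduled step after screening would bring one to light. Items 18.a and 18.b state no contraception requirement. Followed as written, the schedule lets a woman with an unrecognised pregnancy begun in period 1 or the washout start spironolactone at week 10. What is at stake is participant safety; power, type I error and the treatment comparison are not affected.

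**Working it through.** The plan gives no figure of its own to reproduce. The check is date arithmetic on Table 2, followed by a rough count of the women concerned.

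**Age of the test.** Inputs from Table 2: screening at week −1 or −2; dispensing at weeks 0 and 10; last visit at week 16. Age of test = visit week − screening week.

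| Time point | Screened at week −1 | Screened at week −2 |
|---|---|---|
| Visit 1, first dispensing | 0 − (−1) = 1 week (7 days) | 0 − (−2) = 2 weeks (14 days) |
| Visit 4, second dispensing | 10 − (−1) = 11 weeks (77 days) | 10 − (−2) = 12 weeks (84 days) |
| Visit 6, end of period 2 | 16 − (−1) = 17 weeks | 16 − (−2) = 18 weeks |

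**What happens at Visit 4.** Table 2 marks a concomitant medication assessment, dispensing, vital signs and serum potassium. No urine sample and no pregnancy test are marked. Items 16.a, 18.a.2 and 18.b.2 agree with this, so the single mark is not an artefact of a damaged table.

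**How many women.** Item 15 gives 62 participants, 50% male, aged 19 to 65.

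- Women: 0.5 × 62 = 31.
- Of childbearing potential, assumed 20 to 50% (not in the document): 31 × 0.2 = 6.2 to 31 × 0.5 = 15.5, or about 6 to 16.
- Amiloride-first, half on average under simple randomisation: 3.1 to 7.75, or about 3 to 8.

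**Expected pregnancies between screening and week 10.** The document gives no conception rate; 1 to 10% per year is assumed. With annual rate r over w weeks, the probability is 1 − (1 − r)^(w/52).

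- Low: 1 − 0.99^(11/52) = 0.0021; × 3.1 women = 0.007.
- High: 1 − 0.90^(12/52) = 0.0240; × 7.75 women = 0.19.

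These count all pregnancies under the assumptions. Those still unrecognised at week 10 would be fewer, since some women would know and report it.

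**With a test at Visit 4.** The test would be 0 weeks old at the second dispensing instead of 11 to 12, and 6 weeks old at week 16 instead of 17 to 18.

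**The case against.** The strongest objection is that the full precautions may be elsewhere. Item 19, which asks for precautions and monitoring, tells drug studies to "complete the Drug or Device Review Sheet and skip to question #20". That sheet is not available, nor are the consent pages or Figure 1, and any of them could call for contraception or repeat testing. This stands as a limit on confidence. It does not remove the point: Table 2 is the combined procedure schedule, and a repeat test required elsewhere would have to appear there.

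It can also be said that the safeguard is coherent: pregnancy is excluded at entry, women are warned, and a known pregnancy ends participation. That is true, and the finding is a weakness in the schedule, not a contradiction. The comparison with potassium is also imperfect. Both study drugs raise potassium, so re-checking it has a reason that does not apply to pregnancy. The comparison shows only that week 10 already serves as an entry check.

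Rarity is conceded; the expected number is well below one. The 77 to 84 days is the age of the test, not the duration of an unnoticed pregnancy, and women are also seen at weeks 2 and 6. The main risk is therefore a recent conception that the woman does not yet know of.

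Finally, a week-10 test would not find every case. It could miss a very recent conception. It does nothing for spironolactone-first women who conceive during period 1, or for amiloride-first women who conceive after week 10. It prevents most of the avoidable exposures at the second start, not all exposure.

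**Conclusion.** The concern holds. The document fixes one pregnancy test, at screening, and by the schedule's own dates that test is 11 to 12 weeks old when amiloride-first women are first given spironolactone. Between the two, detection rests on the woman recognising and reporting a pregnancy.

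The size is small: roughly 3 to 8 women, with 0.007 to 0.19 expected pregnancies among them by week 10. Those counts rest on the assumed childbearing share and conception rate; the age of the test rests on Table 2 alone. The case for change is the seriousness of the harm and the low cost of reducing it, not its frequency. The change should be made, with confidence held at medium because the Drug Review Sheet is unseen.

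**What to change.** In Table 2, add a urine pregnancy test at Visit 4, read before drug is dispensed, for every woman of childbearing potential. In item 18.a.2, add a sentence stating that a positive result bars entry to the second treatment period. Apply it in both sequences: treatment is double-masked, so site staff cannot tell who is about to start spironolactone. A test at Visit 1 is optional, since the screening result is then only one to two weeks old. If the Drug Review Sheet already requires a repeat test, align Table 2 with it.

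The cost is about 6 to 16 inexpensive tests over the whole trial under the assumed childbearing share, or twice that if Visit 1 is included. Visit 4 currently has no urine collection, so a sample must be added, but there is no extra visit and no extra staff.
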